In this context, in order to define the role of Ivabradine in patients with residual angina after PCI, we aimed to quantify the clinical benefits of adding ivabradine to standard antischemic therapy, in symptomatic patients for residual myocardial ischemia after PCI, using more precise indicators of oxygen consumption.

Furthermore, we studied the effects of ivabradine on diastolic function (both at rest and after exercise) and on the ventricular remodeling.

METHODS.

We investigated the efficacy of treatments with Ivabradine in addition to full anti-ischemic therapy (as per guidelines) compared with the latter alone in patients with signs or symptoms of residual angina underwent percutaneous coronary intervention plus stent implantation. The main purpose was to evaluate if addition of ivabradine to standard therapy might increase the threshold for angina improving the stress tolerance and exercise duration in terms of double product (DP) and triple product (TP), respectively calculated as a product between HR and systolic blood pressure and the product between DP and ejection time. In our opinion these, indirectly, reflect the true myocardial oxygen consumption (MVO₂) and the improvement of mechanical load that the ventricle can withstand at different levels of exercise. Triple product is closely related to the tension-time index, a measure of ventricular work and oxygen demand that is found by multiplying the average pressure in the ventricle during the period in which it ejects blood by the time it takes to do this [10].

The second objective was to evaluate changes at rest and after the stress test of diastolic function and ventricular remodeling, using echocardiographic parameters.

Study Population

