All patients with CCS I-III angina, were considered and only patients who met the inclusion criteria, after signing the informed consent form, were included in our study. The treatment was assigned on the basis of a 1:1 ratio to receive Ivabradine 5 mg twice daily (Ivabradine Group, IG) or standard therapy according to the guidelines (Control Group, CG). Both therapeutic strategies were titrated to the maximum tolerated dose, in particular β -blockers. All patients were submitted to clinical evaluation and exercise stress echocardiography at enrollment time (T1) and after 30 days of therapy (T2). During the period between exercise stress tests, clinical evaluation with ivabradine therapy up-titration was performed after 15 days.

Patient evaluation included physical examination, HR measurement by 12-lead electrocardiograms (ECG), two-dimensional, Doppler and Tissue Doppler echocardiography, using Philips iE33 system (Andover, Massachusetts, USA) and a supine bicycle ergometer stress test. During the test, operators recorded echocardiograms before and during the exercise. The parameters measured were: left ventricular (LV) 2D diameters, systolic function parameters, ejection time, LV end-systolic and end-diastolic volumes in relation to body surface area (end-diastolic and end-systolic indices [EDI and ESI]), and LV ejection fraction (LVEF) were assessed according to Simpson's method (as suggested by the American Society of Echocardiography and European Association of Echocardiography) [11].

Bicycle Stress Test. Exercise test, was performed using a semi-recumbent and tilting bicycle ergometer (X-SCRIBE EKG Analysis, Mortara Instruments; Ergometrics 800s, Ergoline West-Germany) with an initial workload set at 25 Watt and increments of 25Watt/ 2 min. HR and rhythm is continuously recorded using a 12-lead electrocardiogram, blood pressure was measured at baseline, at peak exercise, and during the last minute of each stage including recovery.

The rate of exercise, which was measured in metabolic equivalents (1 metabolic equivalent = 3.6 ml/kg/min), and the duration of exercise were assessed as well.

Chronotropic reserve was estimated using the formula: $100 \times (\text{peak HR} - \text{resting HR}) / (220 - \text{age}) - \text{resting HR}$.

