Stress test was interrupted if the patient developed chest pain, ST segment elevation > 0.1 mV at 80 ms from the J point, or a significant adverse event (significant ventricular arrhythmia, limiting breathlessness, dizziness, muscular exhaustion, chest pain, arterial pressure drop ≥ 10 mmHg with symptoms, or severe systemic hypertension).

Echocardiography. Images were acquired in standard views and displayed side by side in a quad-screen format. All images were digitally recorded in continuous-loop format. Total work at the ischemic threshold and peak exercise were calculated. Double product (DP) was calculated during the last stage of exercise performed by multiplying maximum systolic BP by maximum HR; triple product (TP), was obtained integrating DP with ejection time (ET) measured with mitral annular PW-TDI (BP x SBP x ET).

In addition diastolic function was evaluated by PW Doppler E and A waves, TDI derived E' measurements and E/E' ratio. Mitral annular E' velocity was estimated as the average between lateral and septal velocity.

Drugs with possible interactions with ivabradine such as non-dihydropyridine calcium channel blockers, class I antiarrhythmics and strong inhibitors of cytochrome P450 3A4, were not allowed, whereas short-acting nitrates were allowed up to 3 hours before exercise or after exercise if needed. At the end of the tests, double, triple products and diastolic function evaluation, were collected by a blind operator.

All parameters recorded and calculated in off-line analysis were included in our register.

Statistical analysis.

The sample size was not calculated because it was a pilot study. Continuous variables were presented as mean \pm standard deviation (SD) and categorical variables as percentages. Categorical variables were compared among groups using the chi-square test or Fisher's exact test when appropriate, whereas continuous variables were compared with Student t-test. All tests were two-sided and a *p* value less than 0.05 was considered statistically significant. All analyses were performed using SPSS software, version 20.0 for Windows.

COMPLIANCE WITH ETHICAL STANDARDS

All authors declare that they have no conflict of interests. No funding was received for this study.

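### The t-test leaves the T1 measurement unused or its use unstated, and no between-arm difference or confidence interval is planned; a T1-adjusted comparison and one named main variable would fix this

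*Combined protocol and SAP*

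**What the plan says.** The end of the Introduction states the aim: "we aimed to quantify the clinical benefits of adding ivabradine to standard antischemic therapy". Under Methods, the main purpose is to raise the angina threshold, "improving the stress tolerance and exercise duration in terms of double product (DP) and triple product (TP"). A lower-ranked objective follows: "The second objective was to evaluate changes at rest and after the stress test of diastolic function and ventricular remodeling". No variable is called primary.

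Under Study design and Treatment, all patients have "exercise stress echocardiography at enrollment time (T1) and after 30 days of therapy (T2"), with allocation 1:1. T2 is therefore the only stress echocardiogram after treatment starts, and each outcome has a T1 counterpart.

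The Statistical analysis section describes continuous variables by mean and SD and categorical variables by percentages. It compares continuous variables with a Student t-test, and its decision rule is "All tests were two-sided and a *p* value less than 0.05 was considered statistically significant". It names no contrast, baseline adjustment, between-arm difference, confidence interval, multiplicity rule or exploratory label. The word pilot appears once, as the reason for not calculating a sample size.

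Two definitions bear on the choice of main variable. DP is taken at the end of exercise: "Double product (DP) was calculated during the last stage of exercise performed by multiplying maximum systolic BP by maximum HR". For DP and TP, Methods says they are "respectively calculated as a product between HR and systolic blood pressure and the product between DP and ejection time", whereas the Echocardiography paragraph gives the TP formula with ejection time "measured with mitral annular PW-TDI (BP x SBP x ET").

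**The concern.** Three gaps meet in one short paragraph.

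- **Contrast and precision.** A t-test on T2 and a t-test on change from T1 both fit the wording. They can give different verdicts on the same data, and both are less precise than a comparison that adjusts for T1. In a pilot without a planned sample size, precision is scarce.
- **Estimation.** An aim to quantify benefit calls for an estimated difference and its uncertainty. From means, SDs and numbers per arm, a reader could derive an unadjusted T2 difference with its interval. An interval for the change or for the T1-adjusted difference also needs the T1-T2 correlation, which the plan does not report.
- **Main claim.** At least two variables, DP and TP, serve the main purpose, and each test is judged separately at 0.05. If significance on any one of them, by any contrast, were read as support for the main purpose, the false-positive risk of that claim would exceed 5%.

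**Working it through.** The plan gives no sample size, SD, effect size or correlation, so its only design figure is the 0.05 level. One prespecified test holds that level: simulated error for a single t-test was 4.9 to 5.1%.

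**Assumed inputs (not in the documents):** 15 or 30 patients per arm; T1-T2 correlation ρ of 0.5 or 0.8; DP-TP correlation r of 0.8 or 0.9 (high because TP contains DP), with r = 0 as the extreme; normal data with equal variances.

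**Step 1. Precision.** Relative to a T2 t-test, the large-sample variance is 2(1−ρ) for the change score and 1−ρ² for ANCOVA. With n per arm, estimating the slope multiplies the ANCOVA variance by about 1 + 1/(2n−4). That is 1 + 1/26 = 1.038 at n = 15 and 1 + 1/56 = 1.018 at n = 30.

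| n per arm | ρ | ANCOVA variance | Change-score variance | Cut against T2 | Cut against change |
|---|---|---|---|---|---|
| 15 | 0.5 | 0.75 × 1.038 = 0.779 | 1.0 | 22% | 22% |
| 15 | 0.8 | 0.36 × 1.038 = 0.374 | 0.4 | 63% | 6.5% |
| 30 | 0.5 | 0.75 × 1.018 = 0.763 | 1.0 | 24% | 24% |
| 30 | 0.8 | 0.36 × 1.018 = 0.366 | 0.4 | 63% | 8% |

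Without the small-sample factor, the cuts are 25 to 64% against T2 and 25 to 10% against change.

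The 95% CI half-width of a T2 t-test, in SD units, is t × √(2/n):
- n = 15: 2.048 × 0.365 = 0.75. Under ANCOVA, 2.052 × √(0.1333 × 0.779) = 0.66 at ρ = 0.5, and with 0.374 in place of 0.779, 0.46 at ρ = 0.8.
- n = 30: 2.002 × 0.258 = 0.52. Under ANCOVA, 0.45 and 0.31.

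**Step 2. Power at an assumed true effect of 0.5 SD (simulated; T2 t-test / change t-test / ANCOVA).**
- n = 15: 26/26/32% at ρ = 0.5; 26/56/58% at ρ = 0.8.
- n = 30: 48/48/59% at ρ = 0.5; 48/85/88% at ρ = 0.8.

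In the same trials, the T2 and change t-tests disagree on significance in 27% (ρ = 0.5) and 45% (ρ = 0.8) at n = 15, and in 34% and 46% at n = 30.

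**Step 3. Error for the main claim if any one significant result sufficed.**
- DP or TP, one contrast, two-sided 0.05 each: 1 − 0.95² = 9.75% at r = 0, 7.8% at r = 0.8 and 7.0% at r = 0.9 (bivariate normal).
- One variable, either contrast: under the null, the T2 and change statistics correlate at √((1−ρ)/2), which is 0.50 at ρ = 0.5 and 0.32 at ρ = 0.8. The same calculation gives 9.1% and 9.5%; simulation gives 9.1 to 9.6%.
- DP or TP, either contrast (simulated, r of 0.8 to 0.9): 12.8 to 14.7%.
- Both DP and TP required, one fixed contrast: at most 5%.

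**The case against.** A reader might infer that the plan's error rate is above 5%. The documents do not support that. The excess arises only under an either-suffices rule, and none is stated. Methods names DP and TP together; if both had to be significant on a fixed contrast, error would not exceed 5%. What stands is that the plan states neither rule, so the reader cannot tell which applies.

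A reader might also take the 27 to 46% disagreement as a sign of unreliable results. It assumes a real 0.5 SD effect and is not a false-positive rate. At ρ = 0.8 it is mostly a power gap: of the 46.0% at 30 per arm, 41.7 points are significant on change only and 4.3 on T2 only. It shows that the contrast matters, and no more.

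Nor is the t-test invalid. A t-test fixed in advance on T2, or on change, holds 5%. The case for ANCOVA is efficiency on data already collected.

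Pilot status is the strongest defence. A single error-protected primary is a confirmatory standard, and the plan promises no confirmatory claim. That lowers the weight of the multiplicity part. It does not remove the point, because the same paragraph calls every p below 0.05 significant, attaches no exploratory label and plans no intervals, which are what a pilot most needs.

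Finally, the mismatch in the TP formula may be a slip, since the same sentence builds TP from DP and ejection time. It matters here only because TP cannot serve as the main variable until the two definitions agree.

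**Conclusion.** The point holds, mainly as a better analysis available at almost no cost. Adjusting for T1 would cut the variance of the between-arm difference by about 22 to 63% against a T2 t-test (64% is the large-sample limit) and by about 6.5 to 24% against a change-score t-test. It would also fix the contrast and supply the estimate that the aim calls for. These figures rest on the assumed correlation of 0.5 to 0.8 and 15 to 30 patients per arm.

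The multiplicity part is conditional: about 7 to 10% if either DP or TP sufficed, and about 13 to 15% if the contrast were also free. It supports naming one main variable or labelling the results exploratory. It does not show that the plan exceeds 5%. The change should be made; pilot status keeps it from being essential.

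**What to change.** In the Statistical analysis section:

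1. Analyse each continuous stress-echocardiography outcome as the between-arm difference at T2 adjusted for its own T1 value (ANCOVA), with a 95% CI.
2. Name one main-purpose variable and its direction of benefit, and apply p<0.05 to it alone. Candidates already recorded are exercise duration, total work at the ischemic threshold, last-stage DP, and TP once the Methods and Echocardiography formulas are reconciled. Direction needs particular care for DP and TP: DP contains heart rate, which the Introduction says ivabradine selectively lowers, while the main purpose is greater exercise tolerance.
3. Label all other results exploratory and report them as differences with 95% CIs.
4. As an acceptable alternative for a pilot, name no primary, label every result exploratory, and report ANCOVA differences with 95% CIs.
5. If data have already been seen, disclose the choice of variable and contrast as post hoc. The text is in the past tense and cites a 2018 article under a 2015 version date, so this needs stating either way. Naming a primary after seeing data would not restore error control.

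The cost is a few sentences and one standard model per outcome, with no new measurements. The downside is that fewer outcomes can be called significant.
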